### Human Safety and Tolerability Data

Over 1100 study subjects have been enrolled in a total of 25 completed human studies, of which 17 were phase I studies (single-dose: n=11; multiple-dose: n=6), six were phase II studies and two were open-label extensions. In these studies, a total of approximately 800 study subjects were exposed to AFQ056 while the remaining subjects received either placebo or an active comparator [AFQ056 Investigator Brochure]. Seven of these studies were in patients with FXS, resulting in exposure to AFQ056 in approximately 300 patients with FXS.

Overall, AFQ056 was safe and well tolerated and the AEs observed throughout the clinical development program of AFQ056 were mostly of mild or moderate intensity and resolved spontaneously. There was only a single serious adverse event (SAE) of psychosis reported in healthy volunteer studies that was suspected to be study drug-related. An additional 13 patients with PD-LID were reported with a drug-related SAE, while none of the patients with FXS developed any SAE (for details see below under SAEs). In two single-ascending CAFQ056A1103, CAFQ056A2101) and two multiple ascending dose studies (CAFQ056A2102, CAFQ056A2120) in healthy volunteers, AFQ056 has been administered up to a maximum single dose of 800 mg (clinical service formulation (CSF)) and multiple dose of 450 mg b.i.d. (CSF) for 10 days preceded by 4 days of up-titration. Based on these four safety and tolerability studies a single maximum tolerated dose (MTD) of 400 mg and multiple MTD of 150 mg b.i.d. has been determined. Single doses of >400 mg or multiple doses of >150 mg b.i.d. resulted in drug-related adverse events (AEs) that were considered to be dose-limiting (e.g. hallucinations, psychosis-like symptoms, dyskinesia). Visual hallucinations or illusions were also reported at the multiple MTD of 150 mg b.i.d. (CSF) in chronic smokers (CAFQ056A2109), but not in non-smoking subjects at this dose level (CAFQ056A2102) suggesting that smokers exhibit reduced tolerability to AFQ056 compared to non-smokers. In patients with FXS, AFQ056 has been administered up to 100 mg b.i.d. over duration of over 2 years.

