#### **6.3.9 Clinical Assessments**

Appropriate qualified site staff will be qualified to administer standardized measures and will be trained on all assessments at an investigator meeting held before the study is initiated, or at the study site or by web -based training if the assessor is not able to attend the investigator meeting.

**Vital Signs** - Height (cm), weight (kg) and vital signs, including blood pressure (SBP and DBP in mmHg), heart rate (bpm), and body temperature (°C) will be assessed at all study visits. These will be recorded in the source documents and CRFs.

**Physical and Neurological Examination** will be performed at all study visits. It will include the examination of general appearance, skin, neck (including thyroid), eyes, ears, nose, throat, lungs, heart, abdomen, back, lymph nodes, and extremities. The neurological exam will include examination of cranial nerves, strength, deep tendon reflexes, sensory exam, cerebellar functions, and gait. Results of all physical and neurological examinations will be documented in the source documents and the CRFs. Significant abnormalities of the physical and neurological exam (not expected based on the diagnosis of FXS itself) that are present prior to the start of the study drug will be listed as a prior diagnosis in the medical history as current medical conditions in the source documents and CRFs. Significant findings identified after the start of study drug which meet the definition of an adverse event must be recorded as an adverse event in the source documents and CRFs.

**Funduscopic Examination** will be performed at Screening, -2 month visits, AFQ Baseline and 2, 4, 8, 10, 12, and 16 month and follow up visits (visits 1, 2, 3, 5, 7, 9, 11, 12, 14 and 15) by the PI (fragile X specialist). This will be done to screen for retinal abnormalities based on retinal degeneration findings observed in a 2-year rat carcinogenicity study conducted by Novartis. If any abnormal findings not previously documented in the history or any significant changes in the exam occur at any time during the study, the patient will be referred for evaluation and care in Ophthalmology.

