## 9.7 Safety Analysis

Secondary analyses to examine long-term safety of AFQ056 in this cohort of young children with FXS will be done as follows. Frequencies of adverse events occurring throughout the entire treatment period (both clinical and laboratory) will be tabulated and compared between the active drug and placebo groups during the placebo-controlled period of the study (8 months) and compared across the entire study duration divided based on treatment-assignment at the time of the AE. **Low frequency AEs occurring in less than 5% of the cohort and those that are not different between the drug and placebo groups by visual inspection will not be analyzed further.** Higher frequency events for which statistical comparison would be possible and that appear to be occurring at different frequencies between the drug and placebo groups for either set of comparator groups will be formally compared statistically using a chi-squared analysis. Longitudinal analyses will be done for AEs occurring more frequently in the AFQ056-treated group to determine if there is an increase over time of treatment in these AEs.

[figure not shown]
AFQ056 for Language Learning in Children with FXS

Version v15

Version date 02/03/2021

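### Section 9.7 bars further analysis of any adverse event seen in under 5% of the pooled cohort or judged equal by eye, so a 4-versus-0 split gets no estimate, interval or formal comparison

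*Combined protocol and SAP*

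**What the plan says.** Section 9.7 starts with a full tabulation. Frequencies of clinical and laboratory AEs "will be tabulated and compared between the active drug and placebo groups during the placebo-controlled period of the study (8 months"), and are also "compared across the entire study duration divided based on treatment-assignment at the time of the AE".

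Two screens follow. The first removes "Low frequency AEs occurring in less than 5% of the cohort". The second removes "those that are not different between the drug and placebo groups by visual inspection will not be analyzed further". The more frequent events, where a comparison is judged possible and the groups appear to differ in either comparator set, are to be "formally compared statistically using a chi-squared analysis". No significance level, continuity correction, exact alternative or definition of the cohort denominator is given.

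Section 9.5.3 (Safety Endpoints) also covers AEs. It says the numbers of AEs and serious AEs will be compared statistically between the groups, with no frequency screen, and that AEs will be tabulated descriptively by arm. The opening of Section 9 leaves a formal statistical analysis plan to be written later.

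**The concern.** A rarity cut on the pooled cohort ignores how the cases divide. Four cases split 2 and 2 are treated the same as four cases all on drug, although only the second suggests harm.

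The visual screen is applied to results by arm, so the data decide which events get a p-value. A reader of the final report could not tell how many terms were looked at and passed over.

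The protocol gives safety real weight. Section 2.1 says there is no extended safety data in young children and makes a chronic safety profile one purpose of the extension. Section 6.3.9 schedules funduscopy to look for "retinal abnormalities based on retinal degeneration findings observed in a 2-year rat carcinogenicity study". In a trial of 50 per arm, uncommon events can be described only by an estimate with its uncertainty, and the rule withholds that.

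**Working it through.** The plan states no power, alpha or sample size for AE comparisons, so there is no figure to reproduce. Inputs: 100 children randomized 1:1, so 50 per arm (Section 9.1); the 5% cut and the chi-squared test (Section 9.7); 20% dropout (Section 9.8); AE rates in Section 2.2, Table 4. Counts are children affected. A two-sided 0.05 level is assumed.

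**1. What the cut removes.** 5% of 100 is 5, so totals of 0 to 4 are screened out. A 4-versus-0 event is 4/100 = 4.0%. With 45 per arm it is 4/90 = 4.4%, still removed. With 40 per arm it is 4/80 = 5.0%, not below 5%, so kept.

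**2. How often it removes a real excess.** With X ~ Binomial(50, p) on drug and no placebo events, the probability is P(X ≤ 4):
- 8% risk on drug: 0.629
- 5% risk on drug: 0.896
- 6% on drug and 1% on placebo (sum of two binomials, total ≤ 4): 0.728

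**3. What is lost for 4 versus 0.** Fisher two-sided p = 2 × C(50,4)/C(100,4) = 2 × 230,300/3,921,225 = 0.117. Mid-p is half of this, 0.059. Uncorrected chi-squared = 100 × (4 × 50)² / (4 × 96 × 50 × 50) = 4.17, p = 0.041; with Yates correction p = 0.126. Exact 95% limits are 2.2% to 19.2% for 4/50, with an upper limit of 7.1% for 0/50. For the risk difference of 8 points, the Wilson limits are 3.15% to 18.84% (4/50) and 0% to 7.13% (0/50). The score-based (Newcombe) interval is 8 − √(4.85² + 7.13²) = −0.6 to 8 + (18.84 − 8) = 18.8 percentage points.

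**4. Chi-squared for events that pass.** The expected count per arm is half the total: 2.5 to 4.5 for totals of 5 to 9, and at least 5 from a total of 10.

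| AFQ056 vs placebo (of 50 each) | Expected per arm | Chi-squared, uncorrected | Yates | Fisher | Mid-p |
|---|---|---|---|---|---|
| 5 vs 0 | 2.5 | 0.022 | 0.066 | 0.056 | 0.028 |
| 6 vs 0 | 3.0 | 0.012 | 0.035 | 0.027 | 0.013 |
| 7 vs 1 | 4.0 | 0.027 | 0.065 | 0.059 | 0.033 |
| 8 vs 2 | 5.0 | 0.046 | 0.096 | 0.092 | 0.054 |

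Exact type I error of the uncorrected test at 0.05, after the five-event screen and summed over all tables at 50 per arm, is 0.022, 0.049, 0.055 and 0.052 at common event rates of 5%, 10%, 15% and 20%. Fisher's test gives 0.007 to 0.028 over the same range.

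**5. Illustration from Table 4** (100 mg bid, N = 84, versus placebo, N = 86; adults and adolescents, 12 weeks). Expected total at 50 per arm = 50 × d/84 + 50 × c/86, where d and c are the numbers affected on drug and placebo.
- Nausea (4 vs 0): 2.4; agitation and irritability (3 vs 0 each): 1.8; self-injurious behavior (2 vs 0): 1.2. The probabilities of falling below the cut are 0.91, 0.97, 0.97 and 0.99.
- Dizziness 6.5, insomnia 8.3, vomiting 7.1 and decreased appetite 5.3 would pass, with expected counts of 2.7 to 4.2 per arm.
- Headache (11.8) and nasopharyngitis (11.2) would have expected counts above 5.

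**The case against.** A reader might infer that sub-5% events are discarded or never compared. The documents do not support that. Section 9.7 tabulates and compares all AEs by arm before the screens apply, Section 9.5.3 repeats the tabulation, and the DSMB monitors AE rates (Section 9.9). A 4-versus-0 event would be visible. It might also be kept through the whole-study comparison, or if the denominator is 80. The whole-study route is a weak rescue: children assigned to placebo later take AFQ056, so one child can count on both sides, which breaks the independence that chi-squared assumes.

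A reader might also infer that the chi-squared p-values are generally too small. That does not stand. Fisher's test is conservative, mid-p lies close to uncorrected chi-squared, the type I error stays at or below about 0.055, and Section 9.7 does not say which chi-squared version is meant. What stands is narrower: for totals of 5 to 9, the unspecified choice of test can move a result across 0.05.

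Nor do the documents show that the rule strips out this drug's gravest risks. In Section 2.2 the events that "resulted in drug-related adverse events (AEs) that were considered to be dose-limiting (e.g. hallucinations, psychosis-like symptoms, dyskinesia") followed single doses above 400 mg or multiple doses above 150 mg b.i.d., while this protocol's highest level is 100 mg BID. Seizure is not given as an AFQ056 risk. Insomnia and behavioural activation are expected to be relatively common. Serious events also reach the medical monitor individually (Section 9.9) and count towards a trial stopping rule (Section 6.2.3). These routes protect children during the trial, but none supplies a between-arm estimate at its end.

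**Conclusion.** The concern holds in a limited form. As written, Section 9.7 gives no effect estimate, interval or formal comparison for any AE affecting 0 to 4 of 100 children, whatever the split, and chooses the events to be tested from the observed difference. At 50 per arm, an event with 8% risk on drug and none on placebo is screened out about 63% of the time. The loss is of information on size and uncertainty, such as 8 points with an interval of roughly −1 to 19, and not of a significant finding. The chi-squared weakness is confined to totals of 5 to 9 and brings no material error inflation.

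Section 9.5.3, with no screen, conflicts with Section 9.7 unless it means overall totals only, which it does not say.

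These figures assume that the cohort is all 100 randomized children and that safety tests use 0.05; neither is stated. The Table 4 projection comes from older patients at one dose and is only illustrative.

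**What to change.** In Section 9.7, and in the formal analysis plan before any results by arm are seen:

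- Delete the 5% and visual-inspection screens.
- For every AE term in the 8-month blinded phase, report n, % and the AFQ056 minus placebo risk difference with an exact or score 95% confidence interval.
- Do this whatever the frequency for a list named in advance from the protocol's own text: hallucination or psychosis-like symptoms, dyskinesia, visual or retinal findings, insomnia, and behavioural activation. Leave out seizure.
- If p-values are shown, use Fisher's exact or mid-p where expected counts are below 5.
- Reconcile Section 9.7 with Section 9.5.3, stating which counts are compared and on what denominator.

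The cost is wording and a longer table. Some chance imbalances will appear among the intervals, and the report should say so.

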## 9.8 Sample Size and Accrual

Estimated required sample size was calculated for the primary endpoint of language. Data from the observational study of was used, and additional estimates of effect size (no raw data) were from an unpublished pre-post randomized clinical trial (RCT). Winarni et al. extracted data from chart reviews for 45 FXS children age 12-50 months. Eleven children were treated with sertraline, and the remainder of 34 were not. Variance components of the random effects and error were estimated and sample size was computed using analytic formulas for LMMs. Recall that in the LMM of Equation 1,  $\gamma_1$  is the difference of the slopes, and it is defined as the proportionate increase of the PL slope,  $\beta_1$ , due to the efficacy of TX (if there is any). We write,  $\gamma_1 = \pi\beta_1$ , where  $\pi$  is the *effect proportion*. For example, if  $\pi = 1$ , Equation 1a shows that the TX slope is twice the PL slope, because  $\beta_1 + \gamma_1 = \beta_1 + (1)\beta_1 = 2\beta_1$ . The analysis used the expressive language and receptive language subscales (age-equivalent scores) of the Mullen Scales of Early Learning. The effect proportion ( $\pi$ ) was estimated considering the on-sertraline group ( $N = 11$ ) as a proxy for TX, and the off-sertraline group ( $N = 34$ ) as a proxy for PL. The effect proportion was also estimated using slope estimates from unpublished data in a RCT of sertraline efficacy. The RCT used a pre-post design over 6 months to study the effect of sertraline versus placebo with FXS children with enrolled age of 24-72 months. Estimates of the effect proportion for the Winarni et al. data were  $\hat{\pi} = 1.27, 2.66$  for expressive language and receptive language respectively, and the estimates from the clinical trial were  $\hat{\pi} = 1.43, 1.52$ . For the analysis, power was set to 80%, and Type I error rate ( $\alpha$ ) was determined as the following. Because this is a proof-of-concept (Phase IIa) proposal with a novel design for a critical population (children with FXS), the  $\alpha$ -level was set to allow for a sensitive detection of efficacy, defined as  $\Delta AIC > 0$  (see statistics section above). It can be shown that  $\Delta AIC = \chi^2_1 - 2$ , so that using  $\chi^2_{1,1-0.16}$  as a critical value for the LRT will allow for detection of  $\Delta AIC > 0$ . In addition to  $\alpha = 0.16$ , sample size was calculated with  $\alpha = 0.10$  because this level is often used in Phase II studies. Figure 3 shows the function of  $\pi$  and  $\alpha$ . A filled circle indicates the required  $N$  for the smallest effect proportion among the studies,  $\min(\hat{\pi}) = 1.43, 1.27$  (expressive, receptive). The figure shows that for the combination of the smallest effect proportion ( $\hat{\pi} = 1.27$ ) and the smallest  $\alpha$ , the required single-arm  $N = 50$  (expressive language). We consider this to be an upper bound on the required sample size, so that a total of  $N = 100$  (50 in each group) should be more than sufficient to detect any magnitude of efficacy (i.e.,  $\Delta AIC > 0$ ). Because of high parental motivation, the dropout rate is anticipated to be very low. However, the  $\alpha = 0.16$  panel of the figure indicates that with total  $N = 100$ , power will still be sufficient to detect  $\Delta AIC > 0$  with as much as 20% dropout ( $100 - 0.2 \times 100 = 80$  or 40 in each group for expressive language).

**Figure 3.** Single-arm sample size as a function of effect proportion, type of language measure, and Type I error rate. Filled circles indicate N for the smallest effect proportion among studies.

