This trial protocol will serve as a model for a new generation of similar trials that need to incorporate a learning paradigm to translate targeted treatments from animal models to other genetic neurodevelopmental disorders. Hence, even in the absence of a drug effect for AFQ056 valuable knowledge will still be gained about how to conduct this type of novel trial. If successful, this trial is expected to create a template for a paradigm shift that will change clinical practice and change the process of translation of mechanistically targeted, animal model-based treatments for FXS and for other neurodevelopmental disorders, so as to move the focus of initial efficacy studies from behavior in adults and adolescents to learning and cognition in young children. Without such a paradigm shift, it is entirely possible the benefits of the advances in basic neuroscience and the promise of reversal of disease in animal models will never be realized in humans due to a flawed process of human testing and inability to detect change in adult populations with developmental disorders. This study is the highest priority in translational medicine in the FXS field right now, as it will allow an understanding of whether the animal model data (even when very extensive and reproducible) does not translate directly to humans or whether we have been doing the wrong clinical trials in humans. It is imperative we do this study soon so as not to continue to waste millions of dollars in the FXS and other highly similar genetic neurodevelopmental disability fields doing clinical trials using translational models that are doomed to failure. Whatever the result of this study, it will illuminate the relevance of animal

model data to human translation, and guide the steps in the process of moving from bench to bedside.

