The Weighted Communication Score coded from a standardized play session has been used in cohorts with autism spectrum disorder (ASD) and has been able to measure change in language skills with age and change in language skills in response to an intervention. Although there is not specific data on this measure in FXTS, it is not possible to validate every outcome specifically for FXTS given the rarity of the disorder. Communication and language issues are similar in FXTS and ASD so the measure is likely to perform similarly in response to an intervention in children with FXTS.

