The LMM is estimated with maximum likelihood, which provides unbiased estimates under an ignorable missing data mechanism. The likelihood ratio test (LRT) will be used to evaluate  $H_0$  by comparing the full model of Equation 1 with a reduced model that omits  $\gamma_1$  (cf. Equations 1a and 1b). There is a one-parameter difference among the models, and the LRT test statistic,  $\chi^2_1$ , has an asymptotic chi-squared distribution. Evidence of treatment efficacy is provided when  $\chi^2_1 > \chi^2_{1,1-\alpha}$ , the latter being the upper  $1 - \alpha$  chi-squared quantile, which leads to the rejection of  $H_0$ . An alternative index of efficacy relevant for this proof-of-concept proposal is the difference in Akaike's information criterion (AIC) among the models. The AIC is an unbiased estimator of  $-2$  times the mean expected log likelihood, and the difference in AIC among two models is their statistical distance. Suppose AIC(full) is the sample AIC for the estimated full model of Equation 1, and AIC(reduced) is that of the reduced model that omits  $\gamma_1$ . Smaller AIC values indicate better statistical fit, so evidence of efficacy is provided when  $\Delta\text{AIC} = \text{AIC}(\text{reduced}) - \text{AIC}(\text{full}) > 0$  because the model with  $\gamma_1 > 0$  has better fit than the model with  $\gamma_1 = 0$ .

AFQ056 for Language Learning in Children with FXS

Version v15

Version date 02/03/2021

The open label phase of the study has both groups receiving treatment (see Figure 2). Change during this phase will also be analyzed using a separate LMM. Focus will again be on the PL and TX slope difference, but the intercept difference will be non-zero ( $\square_0 \neq 0$ ) due to the possibility of a treatment effect in the treatment phase (i.e., an inequality at the end of the treatment phase). The group slope difference might not be statistically significant if the PL group catches up to the TX group during the open label phase. Therefore, the open label phase analysis is considered exploratory.

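### Section 9.8 says 100 children suffice for any size of effect, but on its own inputs 80% power needs a treated slope 2.27 times placebo (about 2.15 times under delta-AIC>0)

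*Combined protocol and SAP*

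**What the plan says.** Section 9.8 (Sample Size and Accrual) presents its calculation as being for the primary language endpoint. It writes the slope difference as a proportion, pi, of the placebo slope, so pi = 1 means that the treated slope is double the placebo slope. Power is 80%, with alpha of 0.10 and 0.16; the latter approximates the rule delta-AIC>0. Section 9.6.1 introduces that rule: "An alternative index of efficacy relevant for this proof-of-concept proposal is the difference in" AIC between the models with and without the slope difference.

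Four estimates of pi come from two sertraline studies: 1.27 and 2.66 from a chart review, 1.43 and 1.52 from a randomised trial. The required number is read from Figure 3 "for the smallest effect proportion among the studies". At pi = 1.27 and alpha 0.10 it is 50 per arm. The section then says "We consider this to be an upper bound on the required sample size" and concludes that 100 in total "should be more than sufficient to detect any magnitude of efficacy", glossed as delta-AIC>0. It adds that at alpha 0.16 a 20% dropout, leaving 40 per arm, still gives enough power.

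On the data source: "The analysis used the expressive language and receptive language subscales (age-equivalent scores) of the Mullen Scales of Early Learning". On the weighted communication score, which is the primary outcome, section 9.5.1 says: "Although there is not specific data on this measure in FXTS" (abbreviation as printed).

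**The concern.** A sample size solved for one effect at 80% power has lower power for every smaller effect, so it cannot cover any magnitude. Fifty per arm is the largest number needed over the four sertraline point estimates, not over the effects the drug might have.

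The labels make the anchor itself uncertain. The value 1.27 is first given as the expressive estimate; the two minima are then printed as 1.43 for expressive and 1.27 for receptive; finally 1.27 and 50 per arm are tied to expressive language.

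What is at stake is how a null result is read. Section 2.1 says of the study that "it will allow an understanding of whether the animal model data (even when very extensive and reproducible) does not translate directly to humans", or whether the wrong trials have been run. Sections 1 and 9.1 call the trial a definitive test of the mGluR theory. Beside a claim of sensitivity to any effect, a null result would look like evidence of no benefit. On the plan's own inputs the trial would miss a doubled slope 38% of the time at alpha 0.10 (29% under delta-AIC>0), and a slope 50% faster 74% (66%) of the time.

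**Working it through.** **Inputs, from section 9.8 unless noted.** 50 per arm; pi = 1.27; power 80%; alpha 0.10, or delta-AIC>0. Section 9.6.1 specifies a 1-df likelihood ratio test, so the test is two-sided. Allocation is 1:1 (section 9.1). The variance components and placebo slope are not printed and Figure 3 is not available, so the 50 cannot be rebuilt. It is taken as stated, and everything below is scaled from it.

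**Method.** I use a normal test with the standard error (SE) of the slope difference independent of pi. With d the true difference divided by its SE, and c the critical value:

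- power = Φ(d − c) + Φ(−d − c)
- d is proportional to pi × √n

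**Critical values.** At alpha 0.10, c = 1.645 and 80% power needs d = 2.486. Delta-AIC>0 means chi-square above 2, so c = √2 = 1.414, alpha = 0.157, and 80% power needs d = 2.255. At alpha 0.16 exactly, d = 2.246.

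**Check against the plan's other figure.** At pi = 1.27 and alpha 0.16, n = 50 × (2.246/2.486)² = 40.8 per arm. The plan's dropout statement uses 40, where power is 79%. That agrees to rounding, so the scaling fits the plan and the dropout sentence stands.

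**Detectable slope ratio at 50 per arm (80% power).**

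- Alpha 0.10: 1 + 1.27 = 2.27.
- Delta-AIC>0: 1 + 1.27 × 2.255/2.486 = 1 + 1.152 = 2.15.

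**Smaller effects.** Here d = 2.486 × pi/1.27, and n for 80% power is 50 × (1.27/pi)², multiplied by (2.255/2.486)² for delta-AIC>0.

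| True treated slope | pi | Power at 50 per arm: alpha 0.10 / delta-AIC>0 | n per arm for 80%: alpha 0.10 / delta-AIC>0 |
|---|---|---|---|
| 2.27 × placebo | 1.27 | 80% / 86% | 50 / 42 |
| doubled | 1.00 | 62% / 71% | 81 / 67 |
| 75% faster | 0.75 | 43% / 52% | 144 / 118 |
| 50% faster | 0.50 | 26% / 34% | 323 / 266 |

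**What a null estimate would exclude.** The implied SE is 1.27/2.486 = 0.511 of the planning placebo slope. A difference estimated at exactly zero would carry a 90% interval of ±1.645 × 0.511 = ±0.84 of that slope.

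**The label conflict.** The chart-review pair is labelled expressive 1.27, receptive 2.66. The trial pair 1.43, 1.52 has no label of its own.

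- If the trial pair is in the same order, the minima are 1.27 (expressive) and 1.52 (receptive).
- If it is in the reverse order, they are 1.27 (expressive) and 1.43 (receptive).
- Neither gives the printed minima of 1.43 (expressive) and 1.27 (receptive). Those arise if the chart-review labels are swapped and the trial pair runs expressive then receptive. On that reading an expressive-language N of 50 would belong to pi = 1.43.

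**If 50 was read at pi = 1.43.** The 80% points become 2.43-fold at alpha 0.10 and 1 + 1.43 × 2.255/2.486 = 2.30-fold under delta-AIC>0. Power is then 71% / 79% at pi = 1.27, 54% / 63% for a doubled slope, and 22.5% / 30% for a slope 50% faster.

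**The case against.** The strongest reply is that the upper bound is meant over the scenarios examined. Across pi from 1.27 to 2.66 and the two alpha levels, 50 is indeed the largest number. That reading is fair for the sentence alone, but the next step uses the bound to claim any magnitude, which does not follow.

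Second, the text does name 1.27 as the value behind 50 per arm, so the label conflict may be no more than a transposed parenthesis. That is quite possible, but the page cannot settle it. The fix is therefore conditional, and the alternative reading makes power worse.

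Third, the power figures are rescaled from one possibly rounded number. If 50 stands for anything from 45 to 54, the 80% point at alpha 0.10 lies between pi 1.20 and 1.32, and doubled-slope power between 66% and 59%. The figures also count rejections in the wrong direction, which add 0.8 points to the 34%. Both effects are small. The original output would be the better source if it can be found.

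Fourth, the plan discloses its Mullen basis and the lack of data on the primary measure. Section 6.3.9 links the weighted score to communication development in FXS, and section 9.5.1 expects it to be more sensitive than standardised scales. Proxy error could therefore run either way, which supports saying that power on this endpoint is unknown.

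Finally, no passage says outright that a null result would exclude benefit, and the design is described as exploratory and proof-of-concept. That justifies a lenient alpha but not an incorrect statement of sensitivity.

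**Conclusion.** The concern holds. Section 9.8 credits the design with a property it lacks. On its own inputs, 80% power at 50 per arm requires a treated slope 2.27 times placebo at alpha 0.10, or about 2.15 times under delta-AIC>0. That any-magnitude is untrue needs no rescaling, since the calculation is made at a stated pi. The power figures do rest on the anchor of 80% at 50 per arm and pi = 1.27, complete data, a two-sided normal test, and variance components common to all pi. They describe Mullen age-equivalent scores; power on the weighted communication score is not established. The labels for pi conflict within the section. No error is shown in the 50 per arm itself or in the dropout statement.

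**What to change.** 1. Check the original sample-size output to confirm which pi gave 50 per arm, and make the expressive and receptive labels agree in all three places, with the order of the trial pair stated.
2. Delete the any-magnitude and upper-bound wording.
3. If pi was 1.27, replace it with: *50 per arm gives 80% power (complete data) for a treated slope at least 2.27 times placebo at two-sided alpha 0.10, or about 2.15 times under delta-AIC>0 (alpha about 0.157). Power is about 62% / 71% for a doubled slope and about 26% / 34% for a slope 50% faster. A null result does not exclude smaller benefits.* If pi was 1.43, use 2.43 and 2.30 times, 54% / 63%, and 22.5% / 30%. Prefer figures from the original output where it provides them.
4. Add: *The calculation rests on Mullen age-equivalent scores from sertraline data; power on the weighted communication score is not established.*

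The cost is wording in one section and one look-up. The stated power becomes less favourable. The sample size, analysis and decision rule stay as they are.
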